The proposal will focus on 3 specific, high-risk, pediatric ambulatory diagnostic errors each representing a unique dimension of diagnostic assessment: evaluation of symptoms, evaluation of signs and follow-up of diagnostic tests. Adolescent depression (i.e. symptoms) affects nearly 10% of teenagers, is misdiagnosed in almost 75% of adolescents and causes significant morbidity. Pediatric elevated blood pressure (signs) is misdiagnosed in 74-87% of patients, often due to inaccurate application of blood pressure parameters that change based on age, gender and height. Actionable pediatric laboratory values (diagnostic tests) are potentially delayed up to 26% of the time in preliminary investigations and 7-65% in adults, leading to harm and malpractice claims.

We propose to conduct a multisite, prospective, stepped wedge cluster randomized trial testing a quality improvement collaborative (QIC) intervention within the American Academy of Pediatrics' Quality Improvement Innovation Networks (QuIIN) to reduce the incidence of pediatric primary care diagnostic errors. QuIIN is a national network of over 300 primary care practices, ranging from tertiary care academic medical centers to single practitioner private practices, interested in and experienced with QICs. Because many processes are likely to be common across diagnostic errors in outpatient settings, a multifaceted intervention, such as a QIC, has a high likelihood of success and broad applicability across populations. Preparatory inquiries to QuIIN primary care providers suggest high interest in reducing these 3 diagnostic errors and provider agreement with randomization to evaluate diagnostic error interventions.

The purpose of this IRB application is to cover the data analysis of the QIC data generated in this project. The AAP's IRB will cover each individual pediatric clinic, the data collection and the conduct of the study.

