The missed diagnosis of adolescent depression primary outcome measure is defined as the incidence of depression in adolescents  $\geq$ 11 years old compared in intervention versus control practices. This outcome measure was chosen because prior research suggested up to 75% of adolescent cases are missed by primary providers, allowing incidence to serve as a proxy for missed diagnoses. The research team strongly considered using documented depressive symptoms (e.g. poor school performance, interrupted sleep patterns, increased disruptive behaviors, etc.) without appropriate provider identification or referral to mental health evaluation as the missed diagnosis of adolescent depression primary outcome. This metric was not chosen because preliminary data suggested the number of adolescents with symptoms suggestive of depression documented prior to a mental health referral was extremely small. This finding echoes research that pediatricians' use of adolescent and parental chief complaints to identify depressive risk factors consistently under identifies adolescent depression. The process measure for this diagnostic error will be the percent of adolescents screened for depression, a practice recommended for all adolescents by the USPSTF, and feasible and acceptable to primary care pediatricians.

 Table 2: Outcome and Process Measures, and Evidence-Based Tools for Diagnostic Error

 Reduction

Primary Outcome Measure	Process Measures	Evidence-Based Tools
Number of Adolescents Diagnosed with	1 Number of adolescents	1 Patient screening in the
Depression per 100 Adolescent Visits	screened for depression	waiting room
Patients >11 years old with documentation of	with the $PHO_9-M$ per total	2 Triage purse scoring and
major depression or subsyndromal depression	number of adolescents	flagging to facilitate
diagnoses	seen per month	provider recognition
Flevated Blood Pressure Not Recognized by	1 Number of patients >3	1 Triage nurse or FHR
Providers per 100 Elevated Blood Pressures	vears old with blood	flagging of elevated
Measured	pressure checked at triage	blood pressures to
Systolic or Diastolic Blood Pressure > 90 th	per total number of	facilitate provider
percentile for age, gender and height or $>120/80$	patients >3 years old seen	recognition
in >3 years old patients without history of		2. Family notification of
hypertension and none of: 1) provider repeated		elevated blood pressure

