The missed diagnosis of pediatric elevated blood pressure primary outcome is defined as elevated systolic or diastolic blood pressure for age, gender and height without provider recognition per 100 elevated blood pressures measured in intervention versus control practices. The process measure will assess the percent of children  $\geq$ 3 years old receiving blood pressure measurement at triage, as this is standard of care and an endorsed recommendation by the AAP, but not regularly adhered to in all pediatric clinics. The evidence-based tools implemented by the collaborative to help reduce this diagnostic error will involve triage nurse or EHR flagging of elevated blood pressures for provider recognition and family notification of elevated blood pressures.

The delayed diagnosis of actionable laboratory results primary outcome measure is defined as the number of delayed actions, as defined in Table 2, per 100 abnormal laboratory results received in intervention versus control practices. Abnormal values are defined by pediatric reference texts. Since no standard definition of an actionable laboratory 'delay' currently exists, timeliness of follow-up was determined by expert opinion and discussions with primary care practitioners. Delays are defined as greater than 30 days for action on elevated lead levels or microcytic anemia, or greater than 7 days for action on STI treatment, *streptococcal* pharyngitis treatment or elevated or reduced TSH work-up. The process measure for delayed diagnosis of actionable laboratory results will be the number of providers with laboratory results unread or unacknowledged in their EHR inbox for more than 72 hours. The tools implemented by the collaborative will include standing orders for nurse actions when abnormal test results are received. For example, if a patient has a positive Chlamydia test, the nurse will immediately call the patient and schedule the next available visit for counseling and antibiotics. These interventions are based on successful newborn screening QICs at CHAM and QuIIN, and AHRQ's toolkit for improving office-based testing.

QIC Data Collection and Standardization:

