An initial orientation session will teach all practices to identify each of these 3 diagnostic errors via chart review, collect data and reliably enter it into the QuIIN IT system, QIDA. The QIDA system has been used by prior QuIIN projects, is web-based and HIPAA compliant, and QuIIN will take responsibility for data security. QuIIN's project manager has experiencing ensuring accurate and timely data submission for primary care pediatric practices from prior

Practice			
Baseline	QIC Intervention Period		
(One Time Data Collection)	(Monthly Data Collection)		
Missed Adolescent Depression			
50 > 11 year old patient charts who	17 11 year old patient charts who		
visited clinic in prior 6 months.	visited clinic in prior month. Chart		
Chart screened for depression	screened for depression		
diagnosis.	diagnosis.		
Missed Elevated Blood Pressure			
50 2 year old patient charts with	10 2 year old patient charts with		
elevated blood pressure recorded	elevated blood pressure recorded		
at triage. Chart screened for	at triage. Chart screened for		
provider recognition.	provider recognition.		
Delayed Diagnosis of Actionable			
Laboratory Results			
50 patient charts with abnormal	10 patient charts with abnormal		
laboratory results as defined	laboratory results as defined		
above. Chart screened for	above. Chart screened for		
appropriate action within time	appropriate action within time		
guidelines defined above.	guidelines defined above.		
*All charts screened will have the following demographic data recorded: age			

Table 3: QIC Primary Outcome Data Collection for Each

\*All charts screened will have the following demographic data recorded: age, gender and insurance status.

QuIIN QICs.

Practices will collect the primary outcome data by employing EHR based record paper-based review or dependina methods on abilities and interest of local Developing EHRs. data collection tools for both EHR and paper based practices allows for maximum generalizability of lessons learned from this collaborative. These tools will ensure standardized data collection bv disparate were practices and pilot tested with two QuIIN practices. All data collection tools will be pilot tested on paper and beta tested by a

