minimum of 2 Expert Group members (always including the QI Advisor). As described below, data will be checked for outliers or abnormal values and feedback given to practices to ensure consistency across practices. Additional data on providers' abilities to recognize abnormal results, either in mental health, blood pressure or laboratory values, will also be collected as this is an important first step in the diagnostic process. These data are described further in the Data collection section below. QIC leadership will use QIDA entered data to disseminate monthly feedback reports with full transparency and QIC benchmarking to intervention practices. Consented core QI team members from each practice will be able to access their team's data. All practices will report demographic data annually, including patient volume, number and training level of physician or physician assistant-level providers, number of nursing and office staff, university-affiliation, EHR availability, presence of trainees, estimated length of time providers take with patients, and prior self-reported work aiming to improve these diagnostic errors.

Table 3 summarizes the primary outcome data each practice will collect and the types of charts they will screen. Numbers of charts are based on power calculations described below and will be a convenience sample. Adolescents with depression will be identified by monthly chart reviews or EHR data summaries when this diagnosis is mentioned in the problem list or in assessment sections of visit notes. Pediatric elevated blood pressures will be identified by flagging blood pressure measurements at triage or pulling reports from EHR systems. Similar to the depression outcome, provider recognition will be identified when this diagnosis is mentioned in the problem list or in assessment sections of visit notes. Finally, abnormal lab results will be tracked by either EHR laboratory summary reports or laboratory management registry tools, such as those found in the AHRQ toolkit for improving office-based testing, and provider recognition will be identified when a diagnosis is mentioned in the problem list, in assessment

sections of visit notes or if medications are prescribed. Intervention practices will also report process outcomes (Table 2).

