the problem list or patient notes per 100 adolescent visits), 2) missed diagnosis of pediatric elevated blood pressure (elevated systolic or diastolic blood pressure for age, gender and height without provider recognition per 100 elevated blood pressures measured) and 3) delayed diagnosis of actionable laboratory results (number of delayed actions, as defined in Table 2, per 100 abnormal laboratory evaluations received). All of this data will originate from paper or electronic patient charts. For each of the charts screened, the following demographic data will also be recorded: age, gender and insurance status. These data will be entered into QIDA without patient names or birthdates. No PHI will be recorded as part of this dataset that will be collected monthly.

The third set of data submitted will be process measure data for each of the three diagnostic errors described in the grant. These data will be submitted by practices assigned to the related diagnostic error while they are actively intervening on that error (i.e. for 8 months the group randomized to intervene on adolescent depression will collect process measure data on screening for adolescent depression). The three process measures will be 1) the percent of adolescents screened for depression, 2) the percent of children  $\geq$ 3 years old receiving blood pressure measurement at triage, and 3) the percent of providers with laboratory results unread or unacknowledged in their EHR inbox for more than 72 hours. These data will be entered in aggregate into QIDA for each clinic monthly and collected via electronic health record or practice based paper charting methods in each practice.

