The fourth set of data collected will be mini-root cause analyses, which identify patient and systems level factors that could have contributed to 1 diagnostic error monthly. Each practice will examine standardized patient, provider and systems factors that could have led to the specific diagnostic errors identified in this grant. These factors could include 1) patient factors of age, gender, reason for visit, patient comorbidities, language barriers, acute illness, agitation of patient/family, social issues, etc. , 2) provider factors of type of provider, provider level of training, provider fatigue/impairment, personal stressors of providers, provider disagreements, provider knowledge, provider beliefs about the project or the patient, etc. and 3) systems factors of time of visit, clinic milieu during visit (chaotic vs. calm), increased workload, staffing concerns, verbal/written communication, computer software or hardware, non-computer equipment, etc.. These mini-root cause analyses factors will be collected on paper based forms, deidentified and entered into SurveyMonkey. Practices will be encouraged to identify and spread lessons learned to all providers in their practices to prevent future errors.

The fifth set of data collected will be related to providers' abilities to recognize abnormal findings that could relate to the diagnostic errors of interest. As recognition of abnormal findings is key to ultimately making a correct diagnosis, it is important for practices to track and understand if their clinicians are appropriately recognizing abnormal results. These data will be obtained by electronic and paper chart review of the same 10-17 charts per month as the primary outcome measures noted above. They will include: 1) Percent of charts with documentation of patient's systolic and diastolic blood pressure percentiles documented in the record, 2) Percent of charts with documentation of mental health concerns in patient record or 3) Percent of charts with abnormal actionable laboratory results noted as "abnormal" in the patient record. Clinics will only collect these data when they are the intervention or control group for a given measure.

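### The blood pressure denominator is found locally by the same kind of flag that the intervention introduces, and no central check of eligibility is described

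*Combined protocol and SAP*

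**What the plan says.** Table 2 defines the outcome as unrecognised elevated readings per 100 elevated readings. A reading is elevated if it lies beyond the 90th percentile specific to the child's age, gender and height, or beyond 120/80. It counts as missed if none of four recognition items is documented.

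QIC Data Collection and Standardization describes how charts are found: "Pediatric elevated blood pressures will be identified by flagging blood pressure measurements at triage or pulling reports from EHR systems". The same section says the chart numbers come from the power calculation and "will be a convenience sample". Practices may use EHR-based or paper-based review.

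Target Diagnostic Error Outcome Measures lists among the intervention tools for this error "triage nurse or EHR flagging of elevated blood pressures for provider recognition".

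The Table 3 footnote on patient-level data reads "All charts screened will have the following demographic data recorded: age, gender and insurance status". Section 7 repeats it for the monthly charts: "the following demographic data will also be recorded: age, gender and insurance status". None of the six data sets in Section 7 lists the reading or the height. The nearest item is in the fifth set, the percent of charts with "systolic and diastolic blood pressure percentiles documented in the record".

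Section 1 says that misdiagnosis of elevated blood pressure, put at 74-87%, is "often due to inaccurate application of blood pressure parameters that change based on age, gender and height".

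**The concern.** A rate can be compared between arms only if its denominator is formed in the same way in both. Here a chart enters because someone, or some local report, has classified the reading as elevated. This happens every month after randomization, and triage or EHR flagging is also something the collaborative teaches to intervention practices. Randomization and pre-randomization matching do not protect against selection that happens afterwards.

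Three routes to bias are open:

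- **Omission in control practices.** If they find fewer of the readings that providers also overlook, their measured miss rate falls and a real benefit is hidden.
- **Omission in intervention practices.** If their charts are found through the flag that prompts the provider, elevated readings that were not flagged drop out. The measured miss rate falls and benefit is inflated.
- **False inclusion in either arm.** A normal reading flagged in error counts as missed when no recognition item is documented, which raises that arm's rate.

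As the submitted data are described, the analyst could neither see which route operated nor remove charts that did not meet the cut-off.

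**Working it through.** **1. The plan's own figure.** Section 7, Power Analysis, gives a detectable effect of 12 points (13% relative) for this outcome, with ICC 0.1, 10 charts per practice per month, 10-20 practices per arm, two-sided alpha 0.05 and power above 80%. Over the first 8-month phase, m = 10 × 8 = 80 charts per practice. The design effect is 1 + (80 − 1) × 0.1 = 8.9. With 20 practices per arm the effective sample is 20 × 80 / 8.9 = 179.8. At a baseline of 87%, a two-proportion calculation gives a detectable difference of 11.5 points (13.2% relative) and 82.9% power at 12 points. The figure therefore reproduces at the favourable end of the plan's ranges. With 10 practices per arm it is 17.1 points. The figure is used below only as a yardstick.

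**2. Omission, no true effect.** Let π be the true miss rate (Section 1: 74% or 87%). Let r be the chance that a missed elevated reading enters the sample, divided by the chance that a recognised one does. The values of r are assumptions.

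Observed rate = πr / (πr + 1 − π)

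| r | π = 74% | Shift (points) | π = 87% | Shift (points) |
|---|---|---|---|---|
| 1 | 74.0% | 0 | 87.0% | 0 |
| 0.9 | 71.9% | 2.1 | 85.8% | 1.2 |
| 0.7 | 66.6% | 7.4 | 82.4% | 4.6 |
| 0.5 | 58.7% | 15.3 | 77.0% | 10.0 |

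If r = 1 in one arm, the r in the other arm that produces a 12-point difference with no change in recognition is the ratio of odds:

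- π = 74%: (0.62/0.38) / (0.74/0.26) = 0.57
- π = 87%: (0.75/0.25) / (0.87/0.13) = 0.45

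Whichever arm has the lower r shows the lower rate. If r is equal in both arms, selection alone creates no difference here.

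**3. A second illustration, obvious and subtle readings.** Assume 40% of elevated readings are obvious with 50% missed, and 60% are subtle with 90% missed. Let c be the share of subtle readings identified.

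Observed rate = (0.4 × 0.5 + 0.6c × 0.9) / (0.4 + 0.6c)

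This gives 74.0% at c = 1, 71.2% at 0.75, 67.1% at 0.5 and 60.9% at 0.25. With imperfect identification in both arms, 0.75 against 0.5, the difference is 71.2 − 67.1, about 4 points. A 13-point difference needs 100% against 25%.

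**4. False inclusion.** Let f be the assumed share of sampled charts that were not elevated. As an upper bound, count all of them as missed.

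Observed rate = (1 − f)π + f

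At π = 74%, f = 0.1 gives 76.6% and f = 0.2 gives 79.2%. At π = 87% the results are 88.3% and 89.6%. This pushes the rate the opposite way to omission in the same arm.

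**The case against.** The strongest reply is that an arm difference is not shown. The same chart-finding methods, orientation session and standardized, piloted tools apply to every practice, so a control practice may be using the same instrument as an intervention practice. This stands as far as it goes: the documents establish that identification can differ by arm, not that it does. But training standardizes abstraction and does not verify eligibility. The outlier checks in Section 8 cannot test a reading that is not submitted. Section 2 concedes a measurement effect and assumes it is equal between groups, without addressing which readings are sampled.

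The plan also has two partial safeguards. The percentile-documentation measure is collected in both intervention and control practices, so it is an indirect signal of percentile use by arm. It shows that a percentile was written down, not that the reading met the cut-off. Adjustment for baseline error rates absorbs stable differences between practices, but not a change in identification that the intervention causes. In addition, the 120/80 limb needs no height, and an EHR that computes percentiles narrows the gap.

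A reader might infer three stronger things that the documents do not support:

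- **That the readings and heights are not recorded at all.** The lists in Table 3 and Section 7 are labelled demographic, and the collection forms are not in the documents. One can say only that these items are not listed. The readings also stay in local charts and could be abstracted again.
- **That the protocol blames the whole 74-87% on local staff misapplying cut-offs.** It says this is often the cause, and it names no staff group.
- **That a wrongly flagged normal reading always counts as missed.** It does so only if no recognition item is documented.

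**Conclusion.** The point stands as a correctable weakness in one of the three primary outcomes. The denominator is formed after randomization by local flags or reports, flagging is also an intervention tool, and no described data item or central check confirms eligibility. The readings compared may therefore differ between arms.

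The size cannot be derived from the documents. With the assumed inputs above, the bias runs from a few points under mild selection to about the stated 12-point detectable effect under strong selection. The larger figures need near-complete identification in one arm and poor identification in the other. It is tempting to conclude that control practices will overlook subtle readings and that the trial is biased against the intervention by a known amount, beyond repair. The documents fix neither the direction nor the amount, and local charts could be re-checked.

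**What to change.** **Eligibility.** Add systolic value, diastolic value and height to the blood pressure chart form; age and gender are already recorded. Compute percentile status centrally with one algorithm, and restrict the primary denominator to charts that meet the Table 2 cut-off. For charts already collected without these fields, apply the restriction in a sensitivity analysis. If the form already holds these fields, the plan need only say so and specify the calculation.

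**Omissions.** Central calculation removes false inclusions but cannot recover readings that were never submitted. Each practice should therefore use the same chart-finding method in its control and intervention periods, independent of the intervention flag. This can be an EHR report of all triage readings where available, and otherwise a fixed rule such as consecutive eligible visits until the monthly quota of 10 is reached.

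**Cost.** Three fields that are neither names nor birthdates, and one calculation. Some submitted charts will not qualify. The load is heavier on paper: if 10-20% of readings are elevated (an assumption), reaching 10 means looking through 10/0.20 = 50 to 10/0.10 = 100 readings a month, although only qualifying charts need full abstraction. This matters because the design was changed to reduce collection burden, and Section 4 (Study Population) gives difficulty with data collection as one reason practices were lost. Full abstraction of all triage readings is therefore not proposed.
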